Since a significant event in this trial can occur from toxicity from the study drug or disease worsening (e.g., a pemphigus flare), the standard 3 + 3 design rules for dose escalation will not be employed. Therefore, if a Grade 3 or higher AE or any SAE occurs in a subject during his/her first year of study participation, enrollment will be suspended until the SRC can convene to review the event. If this occurs, the SRC may decide to proceed with enrollment, add additional subjects to the cohort, continue the suspended enrollment until the Data and Safety Monitoring Board (DSMB) can review the data, or place the trial on hold. The SRC will review all Grade 3 or higher AEs or any SAEs that occur throughout the study. However, since the likelihood of events being related to the investigational treatment diminishes over time, Grade 3 or higher AEs or any SAEs occurring during a subject's second or third year of the study will not result in an immediate suspension of enrollment, donation, and treatment, unless the SRC determines that such action is indicated. Provided the SRC can review the event within 5 business days of awareness, events judged to be significant will drive protocol management in terms of proceeding, suspending enrollment/treatment pending ad hoc DSMB input, or placing the study on hold pending further evaluation.

DSMB input will be required for the evaluation of some specific events. Description of these events and additional directives are outlined in Section 5.5.4, *Safety Stopping Guidance*.

Accrual of all subjects is expected to take approximately 1.5 years.

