## 3.2 Description of Primary Endpoint

### 3.2.1 Primary Safety Endpoint

The primary study endpoint is the number of significant events in each cohort through Week 52, defined as any related NCI-CTCAE Grade 3 or higher AE or any related SAE.

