#### 5.5.4 Safety Stopping Guidance

The SRC will suspend enrollment after a Grade 3 or higher AE or any SAE (as described in Section 3.1, *Description of Study Design*) in this trial in order to review the event, to review any additional events that occurred in the trial, and to make a decision on how to proceed. In the event of a temporary suspension in enrollment for a Grade 3 or higher AE or any SAE or a post release positive sterility result (see Section 5.3.3, *Action Plan for Post Release Positive Sterility Results*), no new subjects will be consented or started on therapy with PolyTregs; subjects who already received PolyTregs will continue to be followed. Subjects in the screening phase of the study may continue screening procedures (e.g., blood tests), but a skin biopsy to confirm Inclusion Criteria # 3 (see Section 4.1, *Inclusion Criteria*) should be deferred. Enrollment will not occur until the SRC review is complete.

A significant event in this trial can occur either due to toxicity from the study drug or disease worsening (e.g., a pemphigus relapse/flare) assessed as related to the investigational treatment.

The SRC will make this determination, seeking advice from the DSMB, if necessary. After SRC review, the study will: 1) proceed with enrollment as originally planned, 2) continue to suspend enrollment until the DSMB can review and advise on the event, or 3) be placed on hold pending further evaluation of the event, consideration of potential study modifications, and review by the DSMB, IRB and FDA.

For Grade 3 or higher AEs or any SAEs occurring in the first year of the study for each participant, DSMB input will be required for the evaluation of the following events unless the event was judged clearly unrelated to the investigational treatment:

- two Grade 3 or higher AEs or SAEs that occurs during the first 12 weeks of each participant in each cohort
- any Grade 4 or 5 AE
- two or more Grade 3 AEs of the same preferred term in a cohort
- any Grade 3 AE that is part of a pemphigus relapse/flare using the consensus definition of 3 or more new lesions a month that do not heal spontaneously within 1 week or by the extension of established lesions in a patient who has achieved disease control [58]

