For Grade 3 or higher AEs or any SAEs occurring in the second or third years of the study for each participant, DSMB input will be required for the evaluation of the following events unless the event was judged clearly unrelated to the investigational treatment:

- any Grade 4 or 5 AE
- two or more Grade 3 AEs of the same preferred term in a cohort

In addition to the pre-scheduled data reviews and planned safety monitoring, the DSMB will review any event that potentially impacts safety at the request of the SRC or DAIT, NIAID. The DSMB will have the discretion to recommend actions regarding study conduct and continuation as a consequence of any planned or unplanned monitoring activity.

Otherwise, the DSMB will be informed in real time per the following criteria:

- During Year 1 of each subject's participation:
  - any decision of the SRC to add additional subjects based on confirmation of a significant event (as defined as any related Grade 3 or higher AEs or any SAEs)
  - any malignancy
- During Years 2 and 3 of each subject's participation:
  - any Grade 3 event that is part of a pemphigus relapse/flare using the consensus definition of 3 or more new lesions a month that do not heal spontaneously within 1 week or by the extension of established lesions in a patient who has achieved disease control [58]
  - any malignancy

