##### 7.8.3 DSMB Review

The DSMB will review the safety data collected when the fourth subject in cohort 1 completes Week 8. In addition, the DSMB will review accumulating safety data at least yearly during planned DSMB Data Review Meetings. Data for the planned safety reviews will include, at a minimum, a listing of all reported AEs and SAEs. To ensure subject safety between Data Review Meetings, the DSMB will be informed of all expedited safety reports in a timely manner.

In addition to the pre-scheduled data reviews and planned safety monitoring, the DSMB may be called upon for ad hoc reviews or emergency meetings (see Section 5.5.4, *Safety Stopping Guidance*). The DSMB will have the discretion to recommend actions regarding study conduct and continuation as a consequence of any planned or unplanned monitoring activity.

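### Real-time DSMB notice of a Year 1 significant event depends on an SRC decision to add subjects, so an isolated related Grade 3 event can wait for the next planned DSMB review

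*Combined protocol and SAP*

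**What the plan says.** Section 3.2.1 states: "The primary study endpoint is the number of significant events in each cohort through Week 52". A significant event is a related Grade 3 or higher AE or a related SAE, with relatedness determined by the SRC (Section 3.1).

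Under Section 5.5.4, a Grade 3 or higher AE or an SAE suspends enrollment for SRC review. Three outcomes are listed: "1) proceed with enrollment as originally planned, 2) continue to suspend enrollment until the DSMB can review and advise on the event", and, third, a hold pending wider review. DSMB input is then required in Year 1 for four kinds of event unless clearly unrelated. The first is "two Grade 3 or higher AEs or SAEs that occurs during the first 12 weeks of each participant in each cohort". The others are any Grade 4 or 5 AE, a repeated Grade 3 preferred term within a cohort, and a Grade 3 AE belonging to a flare.

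The notification list follows: "Otherwise, the DSMB will be informed in real time per the following criteria". Its Year 1 entries are malignancy and "any decision of the SRC to add additional subjects based on confirmation of a significant event". Its Year 2 and 3 entries are Grade 3 flare events and malignancy.

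The synopsis gives a different set of SRC options: "the SRC may decide to proceed with enrollment, add additional subjects to the cohort", among others. In the matching paragraph of Section 3.1, dose adjustment stands where the synopsis has added subjects.

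Section 7.8.3 schedules a DSMB review when the fourth cohort 1 subject completes Week 8. Beyond that, "the DSMB will review accumulating safety data at least yearly during planned DSMB Data Review Meetings", and expedited safety reports are passed on between meetings.

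**The concern.** The Year 1 bullet reports what the SRC did, not what happened to the subject. The decision it names, adding subjects, is not among the three outcomes in the same section. After a confirmed primary-endpoint event, the SRC may simply proceed, and then this bullet requires no notice.

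What is at stake is independent oversight. The SRC consists of the protocol chair, the coordinating center and the sponsor's division (Section 3.1). The DSMB is the independent body (Section 11.4). In a cohort of 4-6, one affected subject is 1/6 = 17% to 1/4 = 25% of the cohort, so a single event carries weight in judging a dose.

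**Working it through.** **Step 1. Required routes to the DSMB in Year 1 when the SRC confirms an event and proceeds.**

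| Route | Reaches the DSMB | Does not cover |
|---|---|---|
| 5.5.4, required input | Counted pair in first 12 weeks; Grade 4/5; repeated Grade 3 preferred term in a cohort; Grade 3 flare | First, single, non-flare Grade 3 AE; lone SAE below Grade 4 |
| 5.5.4, real-time notice | SRC decision to add subjects; malignancy | Confirmation followed by proceeding |
| 7.5.3 with 7.8.3, expedited reports | Serious, unexpected suspected reactions | Non-serious Grade 3 AEs; expected SAEs, which go to the annual IND report |
| 5.5.4, ad hoc review | Any event, on request of the SRC or the sponsor | Not mandatory |
| 8.4, pause and end-of-cohort reports | SRC | DSMB not named as recipient |
| 7.8.3, fourth cohort 1 subject at Week 8 | Events accrued by then | Later cohort 1 events; all of cohort 2 |
| 7.8.3, routine meeting | Everything, at least yearly | Timing between meetings |

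The class left over is the isolated related Grade 3 AE that is non-flare, not a malignancy, not expedited and not in a counted pair, together with the lone related expected SAE below Grade 4. I read the two-event trigger as counting across a cohort, the reading more favorable to the plan. After Week 12, only a repeat of the same preferred term forms a pair.

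**Step 2. Dosing pace in cohort 2.** Inputs are the rule that the previous subject reaches Week 2 before the next donates (Section 3.1) and the windows in Table 6.1: Week 2 ± 3 days, and donation 14-16 days before infusion.

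- Earliest Week 2: Day 14 - 3 = 11; latest: 14 + 3 = 17.
- Infusion-to-infusion interval if the next donation follows at once: 11 + 14 = 25 to 17 + 16 = 33 days.
- First to sixth infusion: 5 × 25 = 125 to 5 × 33 = 165 days.

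Both are well under a one-year meeting interval. At most five more subjects could be infused before a yearly meeting. That ceiling needs the event in the first cohort 2 subject before the second infusion, minimum spacing throughout, no SRC delay, no second qualifying event and no DSMB meeting in the interval.

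**Step 3. Scale.** Table 8.1 follows from 1 - (1 - p)^n and reproduces in all six cells. For p = 0.1, 0.2, 0.3:

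- n = 4: 0.3439, 0.5904, 0.7599 (stated 0.34, 0.59, 0.76).
- n = 6: 0.4686, 0.7379, 0.8824 (stated 0.47, 0.74, 0.88).

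The probability of exactly one affected subject is n·p·(1 - p)^(n-1):

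- n = 4: 0.29, 0.41, 0.41.
- n = 6: 0.35, 0.39, 0.30.

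Dividing by the matching Table 8.1 value, the share of cohorts with any event that have exactly one affected subject is 85%, 69%, 54% (n = 4) and 76%, 53%, 34% (n = 6). A lone affected subject is therefore not an unusual pattern. These shares assume independent subjects and do not separate flare, Grade 4/5, malignant or expedited events, so they do not measure the gap.

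**The case against.** The strongest reply is that this is a deliberate tiered design: the event suspends enrollment, the SRC reviews it, and defined patterns escalate. Much of that stands. The required-input triggers apply in each cohort, so a reader who infers that cohort 2 has no event-count DSMB review would be wrong; what it lacks is a scheduled mid-cohort review. Nor does the DSMB hear only when the SRC adds subjects. Two of the three Section 5.5.4 outcomes go to the DSMB, and the required-input list binds even when the SRC would proceed.

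Prior experience is also reassuring. In the T1DM study, 0 of 14 treated subjects had a Grade 3 or higher event judged related (Section 1.3.2.1.3). The exact one-sided 95% upper bound is 1 - 0.05^(1/14) = 0.19, below the top column of Table 8.1. The disease differs, so this is only indicative.

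Finally, minimum spacing is unlikely, since each suspension adds time. That is fair, but the timing point does not rest on it alone. Accrual is expected to take about 18 months for at most 12 subjects, on average 18/12 = 1.5 months each. Five such intervals are 7.5 months, still under a year. This is a rough average that treats accrual as infusion and ignores the escalation pause.

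None of this gives the leftover class a required route to the DSMB. Referral on request depends on the SRC or on the sponsor, whose division is represented on the SRC.

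**Conclusion.** The gap is real but narrow. In Year 1, if the SRC confirms a significant event and proceeds, the class identified above has no required route to the DSMB before its next planned review. For early cohort 1 events, that is the review at the fourth subject's Week 8. For later cohort 1 events and all of cohort 2, it is a meeting held at least yearly, so a year is the longest wait and not the expected one.

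Three stronger inferences are not supported:

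- That any confirmed related Grade 3 event can bypass the DSMB. Flares, counted pairs, repeated terms, malignancies and serious unexpected reactions do reach it.
- That Table 8.1's 0.76-0.88 sizes the gap. It is the chance of any significant event at the highest tabulated risk, including events that do reach the DSMB.
- That five further infusions should be expected. That is a ceiling under the conditions in the working.

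The conclusion rests on reading the reporting rules, not on an assumed event rate. It is an oversight improvement worth making, not an error in the analysis.

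**What to change.** In Section 5.5.4, replace the Year 1 bullet with: *any event the SRC confirms as a significant event, together with the SRC's decision*. State that this is notice only and creates no new pause or stopping rule.

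The same bullet for Years 2 and 3 is optional. The primary endpoint ends at Week 52, and Section 3.1 explains the lighter later rules by the falling likelihood of relatedness. Significant events through Week 156 are a secondary endpoint, which is the argument for including it.

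The SRC options in the synopsis, Section 3.1 and Section 5.5.4 should also be reconciled, so that it is clear whether adding subjects is an SRC decision after an event.

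The cost is a short protocol edit and at most one extra notification per confirmed event. No visits or data are added: sites already report SAEs and Grade 3 or higher clinical events within 24 hours (Section 7.5.2), and listings are already produced for the SRC (Section 8.4.1).

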## 5.6 Toxicity Management Plan for Study Product

See Section 5.5.2, *Criteria for Permanent Discontinuation of Study Treatment* for details on when to slow, temporarily discontinue, or permanently discontinue the study drug infusion for toxicities.

### 5.6.1 Infection

Based on the potential for Tregs to have immunosuppressive effects, subjects should be closely monitored for the development of signs and symptoms of infection, particularly opportunistic infections after treatment including reactivation of EBV and CMV.

#### 5.6.1.1 Vaccination

Participants will be advised to obtain and will be offered tetanus, diphtheria, and pertussis (Tdap) and inactivated seasonal influenza vaccinations prior to treatment. Any such vaccination must be completed either prior to day -21, or after Week -2's whole blood donation and before day -7.

#### 5.6.1.2 Herpes Simplex Virus

Infection with Herpes Simplex Virus (HSV), with predominance of mucocutaneous involvement, has been associated with pemphigus [61]. The protocol allows for participation of individuals receiving suppressive anti-viral treatment for orolabial or localized cutaneous herpes simplex infection (see Section 4.2, *Exclusion Criteria #24*). Individuals presenting

with oral erosions or ulcerations at screening will undergo viral culture to rule out active mucocutaneous HSV infection.

#### 5.6.1.3 Epstein-Barr Virus

Assessment for the presence of EBV genomes will be carried out according to the schedule outlined in Table 6.1, *Schedule of Events*. Management will depend on the presence or absence of symptoms and on the viral load.

For those with no or NCI-CTCAE Grade 1 or 2 symptoms judged at least possibly related to EBV reactivation:

- If EBV viral load is undetectable, study proceeds as per Table 6.1, *Schedule of Events*
- If EBV viral load is detectable and  $< 2000$  DNA copies per  $10^6$  PBMCs monitoring of EBV viral load may be increased as determined clinically necessary by the investigator
- If EBV viral load is  $\geq 2000$  DNA copies per  $10^6$  PBMCs monitoring of EBV viral load will be increased

For those with NCI-CTCAE Grade 3 or higher symptoms judged at least possibly related to EBV reactivation:

- If EBV viral load is undetectable, monitoring of EBV viral load will be increased as determined clinically necessary by the investigator
- If EBV viral load is detectable, monitoring of EBV viral load will be increased and appropriate treatment will be considered as determined clinically necessary by the investigator

#### 5.6.1.4 Cytomegalovirus

Assessment for the presence of CMV genomes will be carried out according to the schedule outlined in Table 6.1, *Schedule of Events*. Management will depend on the presence or absence of symptoms and on the viral load.

For those who were seropositive at study entry:

- Subjects whose viral load increases 5-fold between scheduled assessments or is  $> 10,000$  DNA IU/ml at any point during the study will be evaluated for CMV retinitis, pneumonia and gastroenteritis/colitis
- Participants with an active infection may be treated with gancyclovir as determined by the investigator. CMV viral load will be monitored by polymerase chain reaction (PCR) until it is  $< 10,000$  DNA IU/ml

For those who were seronegative at study entry:

- Subjects whose viral load is  $> 2,000$  DNA IU/ml will be evaluated for CMV retinitis as clinically indicated, as well as CMV pneumonia and gastroenteritis/colitis
- Participants with an active infection may be treated with gancyclovir as determined by the investigator. CMV viral load will be monitored by PCR until it is  $< 2,000$  DNA IU/ml

For all subjects:

- If a participant develops any symptoms of the eye, lungs, or intestines consistent with CMV infection, additional blood will be drawn for appropriate laboratory analyses as determined by the investigator. Additionally, for those with visual symptoms, an ophthalmological exam will be performed.

### 5.6.2 Infusion Reaction

Section 5.3.1, *Preparation for Administration* describes the pre-medications required to help prevent infusion reactions and the medications that may be used to treat them.

Patients will not receive systemic glucocorticoids higher than their usual dose such as hydrocortisone, prednisone, prednisolone (Solu-Medrol) or dexamethasone (Decadron) at any time, except in the case of a severe or life-threatening emergency since this may have an adverse effect on T cells. If glucocorticoids are required for an acute infusion reaction, an initial dose of hydrocortisone 100 mg IV is suggested.

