## 5.7 Concurrent Medications and Therapy

- If subjects are on prednisone at the Screening visit, subjects may continue to be treated with stable doses of prednisone not to exceed <25 mg/d until Week 12.
  - After Week 12, prednisone may be tapered at the discretion of the investigator, at a suggested rate of 5-10 mg decrease per month down to 10 mg/d, and then 1-5 mg decrease per month down to 0 mg/d.
  - Prednisone dose may be increased during the study for flares of pemphigus and for conditions that are not related to pemphigus based on the PI's clinical judgment. Increases in prednisone should occur only if absolutely necessary, and are discouraged for reasons other than pemphigus flares during the first 12 weeks of the trial. Stress doses of glucocorticoids may be used when clinically indicated.
- If subjects are on background immunosuppressive/immunomodulatory medications at the Screening visit, subjects should continue to be treated with stable doses of these agents until Week 12 including methotrexate  $\leq 25$  mg/week, mycophenolate mofetil  $\leq 3000$  mg/d, mycophenolic acid  $\leq 1080$  mg/bid, azathioprine  $\leq 200$  mg/d, cyclosporine  $\leq 5$  mg/kg/d, dapsone  $\leq 250$  mg/d and IVIG  $\leq 4$ mg/kg monthly.
  - After Week 12, changes in the above background medications may be made per the investigator's judgment. Thus, one medication may be stopped and another medication started. The dose of any of the medications must not exceed those specified above at any point during the study period.
- If a subject is having increased pemphigus disease activity at any point during the study, they will be treated according to the best clinical judgment of the investigator.
- If subjects are on topical agents at the Screening visit, subjects must continue to be treated with stable amounts (stable percentage and approximate volume) of these agents, including steroids and calcineurin inhibitors, until Week 12. After Week 12, the amount of the topical medications may be altered per the investigator's judgment.
  - Of note, topical medications must be held from the planned biopsy location for one week prior to each scheduled skin biopsy. Topical medications must be held 7 days to skin biopsy on Day 0 and may be resumed after the skin biopsy at Week 1. Topical medications must again be held for 7 days prior to the final biopsy at Week 12, and may be resumed after this procedure.

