## 5.8 Prohibited Medications

Prohibited medications include:

- throughout the duration of the trial:
  - immunosuppressive medications other than those specified in Section 5.7, *Concurrent Medications and Therapy*
  - live attenuated vaccines
- 7 days prior to each skin biopsy at the site of the biopsy:
  - topical steroids, topical calcineurin inhibitors

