### 8.3.3 Mechanistic Analysis

Appropriate descriptive statistics will be computed for the change in level of transferred deuterium-labeled Tregs in peripheral blood and skin from Week 1 at Week 12, changes in disease specific and immunologic biomarkers in peripheral blood and skin from baseline to Week 12, and for the relative frequency of adoptively transferred Tregs in blood and skin at each visit assessment. The mechanistic summaries will be completed using the safety population.

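### Section 5.6.2 bars glucocorticoids above the usual dose outside an emergency while Section 5.7 allows non-emergency prednisone increases; the rule needs reconciling, and later Treg samples need flagging

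*Combined protocol and SAP*

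**What the plan says.** Section 5.6.2, headed Infusion Reaction, bars systemic glucocorticoids, prednisone named among them, above the subject's usual dose "at any time, except in the case of a severe or life-threatening emergency since this may have an adverse effect on T cells". The next sentence deals with the acute reaction: "If glucocorticoids are required for an acute infusion reaction, an initial dose of hydrocortisone 100 mg IV is suggested".

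Section 5.3.1, on preparation for the infusion, has the same bar but neither extends it to all times nor gives an emergency exception.

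Section 5.7, on concurrent therapy, states: "Prednisone dose may be increased during the study for flares of pemphigus and for conditions that are not related to pemphigus", on the investigator's clinical judgment. It adds that increases should be confined to absolute necessity, discourages non-flare increases in the first 12 weeks, and allows stress doses when clinically indicated. It also says of subjects with increased disease activity at any point that "they will be treated according to the best clinical judgment of the investigator". Of the background immunosuppressants, it says that doses "must not exceed those specified above at any point during the study period". Section 5.8 prohibits, for the whole trial, "immunosuppressive medications other than those specified in Section 5.7".

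Section 3.4.2 counts participants who need a prednisone increase before Week 12 and before each later listed visit, as an exploratory efficacy endpoint.

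Section 8.3.3 summarizes the "change in level of transferred deuterium-labeled Tregs in peripheral blood and skin from Week 1 at Week 12", and biomarker changes from baseline to Week 12, in the whole safety population. Sections 8.5.1 and 8.5.3 rule out covariate and additional subgroup analyses because of the sample size.

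**The concern.** A site facing a flare that is not an emergency finds a prohibition in one section and a permission in another. Neither section refers to the other or says which prevails. Two things follow.

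First, sites may differ in what they do. They may also differ in whether they record an increase as a deviation, and Section 10 requires major deviations to be reported. The exploratory count in 3.4.2 would then consist of events that are compliant under 5.7 and, unless they were emergencies, deviations under 5.6.2.

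Second, the protocol itself gives a reason to think that added glucocorticoid could affect the infused cells. Labeled-Treg tracking runs from Week 1 to Week 12, when 5.7 still allows flare increases. The planned summary pools every infused subject, with nothing to show which samples followed an increase. A reader of that summary could not tell whether a low labeled-Treg value came after added steroid.

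**Working it through.** This is mainly a comparison of text. The sections do not define usual dose; here it is read as the subject's established maintenance dose.

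| Situation after infusion | 5.6.2 | 5.7 |
|---|---|---|
| Prednisone raised for a flare, no emergency | barred | allowed if absolutely necessary |
| Prednisone raised for an unrelated condition, no emergency | barred | allowed if absolutely necessary; discouraged in the first 12 weeks |
| Stress dose, no emergency | barred | allowed when clinically indicated |
| Severe or life-threatening emergency | excepted | not closed |

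The first three rows conflict; the fourth does not. Section 5.3.1, read literally, bars all four because it states no exception, although its subject is the day of infusion.

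**Does the heading of 5.6.2 limit the bar to the infusion?** Four features of the wording point the other way:
1. It adds to the 5.3.1 sentence that the bar holds at all times.
2. It names prednisone, the drug whose increase 5.7 permits.
3. Its reason, possible harm to T cells, is not specific to the infusion.
4. It treats the acute infusion reaction in a separate sentence.

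**Arithmetic for scale.** The plan's only sample-size figure is Table 8.1, the chance of at least one event among n subjects, 1 − (1 − p)^n. It reproduces for p = 0.1, 0.2, 0.3:
- n = 4: 0.3439, 0.5904, 0.7599 (stated 0.34, 0.59, 0.76)
- n = 6: 0.4686, 0.7379, 0.8824 (stated 0.47, 0.74, 0.88)

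The point does not depend on that table, but the same formula gives an illustration. The documents give no early-flare rate. Assume that 10% to 30% of subjects have a flare by Week 12 for which an increase is considered. The chance that at least one such subject arises is then:
- cohort of 4: 0.34 to 0.76
- cohort of 6: 0.47 to 0.88
- all 12: 1 − 0.9^12 = 0.72 to 1 − 0.7^12 = 0.99

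One subject is 1/6 = 17% to 1/4 = 25% of a cohort. That is a share of the data and not an estimate of bias.

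**The case against.** The strongest reply is about context. Section 5.6.2 sits in the toxicity plan for the study product, opens by pointing to 5.3.1 and closes on the acute reaction. Sections 5.3.2, 5.5.1 and 5.5.2 also mention glucocorticoids only in relation to infusion reactions. Section 5.7 is the dedicated section on concurrent therapy, 5.8 defers to it, and 3.4.2 shows that increases are expected. On this view 5.6.2 was meant for the infusion period and is loosely worded. That may well be the intent, and many sites may follow 5.7. But the text sets no such limit, so the request to state its scope stands.

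The reply is right to stress that 5.7 is not a free permission: absolute necessity and the 12-week discouragement narrow the gap. They do not close it, because neither is an emergency condition.

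A reader might also infer that 5.7 and 5.8 flatly contradict each other on other immunosuppressants. The documents do not support that. The sentence on increased disease activity is a separate item within 5.7, so it can be read as the specific provision for flares and as part of what 5.8 exempts. What is missing is a statement of whether it is subject to the dose limits and the prohibition.

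On the analysis, a reader might ask for persistence results split by steroid exposure. The case against is sound. The split would rest on a post-infusion event driven by disease worsening, might set one subject against three to five, and would run against 8.5.1 and 8.5.3. Because prednisone use at entry already varies, it would not isolate a steroid effect either.

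**Conclusion.** The contradiction is in the wording and is certain at that level: for a non-emergency increase above the usual dose, 5.6.2 says no and 5.7 says yes under conditions. Its practical reach is limited to those of at most 12 infused subjects for whom such an increase is considered, and the documents give no rate. The primary endpoint definition, the sample size and Table 8.1 are unaffected.

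Three stronger conclusions are tempting but unsupported:
- That sites do treat flaring subjects in opposite ways. This is foreseeable with about four sites, but nothing shows it.
- That rescue of the sickest subjects is blocked. Section 5.6.2 excepts severe or life-threatening emergencies.
- That the persistence summary is biased by 17% to 25%. Those figures are only 1/n. The planned summaries include medians and quartiles, which limit the pull of one subject, and no section says that a steroid-related fall would be reported as poor persistence.

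Pooling in 8.3.3 would occur under 5.7 alone; the conflict could only add variation between sites. The analysis point is therefore modest: samples taken after added treatment should be identifiable.

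**What to change.** 1. Reconcile 5.3.1, 5.6.2 and 5.7 so that one rule governs systemic glucocorticoid above the usual dose, and state whether the 5.6.2 bar is limited to the infusion period. The sponsor decides the rule.
2. State in 5.7 and 5.8 whether the clinical-judgment sentence for increased disease activity is subject to the 5.7 dose limits and the 5.8 prohibition.
3. Add to 8.3.3 a dated listing, through Week 12, of systemic glucocorticoid above the Day 0 dose and of any other added immunosuppressant. In the individual data displays, flag the labeled-Treg and biomarker samples taken afterwards.

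The cost is wording in a few sections at the next amendment and one extra listing. Section 6.1 already has concomitant medications recorded at every visit; this assumes that start and stop dates are captured, which matters because no clinic visit falls between Weeks 2 and 8. No subjects, procedures or subgroup comparison are added, so 8.5.1 and 8.5.3 can stay as they are.
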